3 OBJECTIVES AND ENDPOINTS

3.1 Primary objectives and endpoints

Primary objective 1:

To evaluate the safety and tolerability of HIV-1 CH505 transmitted/founder virus Env gp120 immunogen (CH505TF gp120) adjuvanted with Glucopyranosyl Lipid A - stable emulsion (GLASE) in healthy HIV-1 exposed uninfected (HEU) infants

Primary endpoint 1:

Local and systemic reactogenicity signs and symptoms, laboratory measures of safety, weight gain, and AEs and SAEs

Primary objective 2:

To determine whether vaccination with CH505TF gp120 adjuvanted with GLA-SE initiates B-cell lineages potentially capable of generating a broadly neutralizing antibody response

Primary endpoints 2:

Magnitude of HIV-1 Env gp120, CD4 binding site and V1V2-specific serum IgG binding antibodies, as assessed by BAMA two weeks after the 5th vaccination

Quantification and phenotypic characterization of peripheral B cells capable of binding HIV-1 Env gp120, the CD4 binding site (including differential binding to the I Δ 371 mutant) and the V1V2 binding site, as assessed by flow cytometry two weeks after the 3rd and 5th vaccinations

3.2 Secondary objectives and endpoints

Secondary objective 1:

To evaluate the effect of vaccination with CH505TF gp120 adjuvanted with GLA-SE on antibody responses to the South African Expanded Program on Immunization (EPI) schedule vaccinations

Secondary endpoint 1:

EPI vaccine-specific antibody responses, as assessed by Pediatric Vaccine Multiplex Assay (PVMA) 2 weeks after the 5th vaccination

Secondary objective 2:

To evaluate the ability of the vaccine regimen to elicit HIV-specific nAbs.

Secondary endpoint 2:

Magnitude and breadth of serum neutralization of vaccine-matched viral isolates, and viruses engineered to detect precursors of CD4 binding site and V1V2 antibodies 2 weeks after the 5th vaccination.

Secondary objective 3:

To measure Fc-mediated antibody effector functions

Secondary endpoints 3:

Response rate and magnitude of vaccine-elicited serum binding antibodies to FcR proteins, as assessed by BAMA 2 weeks after the 5th vaccination

Response rate and magnitude of serum Antibody-dependent cellular cytotoxicity (ADCC), as assessed by flow cytometry and/or luciferase assays 2 weeks after the 5th vaccination

Response rate and magnitude of serum Antibody-dependent cellular phagocytosis (ADCP), as assessed by flow cytometry 2 weeks after the 5th vaccination

3.3 Exploratory objectives

Exploratory objective 1:

To compare antibody and B cell responses generated in infants in response to CH505TF gp120 adjuvanted with GLA-SE with adults vaccinated with the same immunogen and same adjuvant on the same schedule (HVTN 115)

Exploratory objective 2:

To characterize B cell lineages and evaluate the amount of B-cell receptor somatic hypermutation

Exploratory objective 3:

To evaluate effects of maternal antibody in cord blood, serum/plasma, and breast milk on the humoral response of infants

Exploratory objective 4:

To evaluate additional vaccine-induced antibody effector functions such as Antibody-dependent neutrophil phagocytosis (ADNP) and/or Antibody dependent complement deposition (ADCD)

Exploratory objective 5:

To measure the kinetics and maturation of the polyclonal antibody response with biophysical measurements (eg, BioLayer Interferometry, Surface Plasmon Resonance)

Exploratory objective 6:

Evaluation of breast milk and fecal microbiome at birth and over time to explore the effect of the microbiome on the development of the immune system and on vaccine immunogenicity

Exploratory objective 7:

To use systems biology approaches (eg, high resolution flow cytometry. transcriptomics, proteomics, metabolomics and/or plasma cytokine/chemokine assessment) to determine whether the pre- and/or postvaccination systemic immune milieu is associated with vaccine immunogenicity.

Exploratory objective 8:

To further evaluate immunogenicity, additional assays may be performed based on the HVTN Lab Assay Algorithm

Exploratory objective 9:

To conduct analyses related to furthering the understanding of HIV, immunology, vaccines, and clinical trial conduct

4 COHORT DEFINITION

Healthy HIV-1—uninfected infants born to HIV-1—infected mothers through caesarian delivery in South Africa. To quantify maternal HIV antibody response, mothers will also be enrolled in the study but will not receive study product.

5 POTENTIAL CONFOUNDERS

Characterization of the safety of the vaccine is susceptible to confounding by adverse events not related to the vaccine that by chance occur more often in one arm of the trial than another. Therefore, analyses involving adverse events will incorporate the reported relationship to product as assessed by HVTN staff.

6 RANDOMIZATION

A participant's randomization assignment will be computer generated and provided to the HVTN clinical research site (CRS) pharmacist through a Web-based randomization system. At the institution, the pharmacist with primary responsibility for dispensing study products is charged with maintaining security of the treatment assignments (except in emergency situations as specified in the HVTN Manual of operations [MOP]).

7 BLINDING

Participants and site staff (except for site pharmacists) will be blinded as to participant treatment arm assignments (eg, vaccine or placebo). Study product assignments are accessible to those HVTN CRS pharmacists, DAIDS protocol pharmacists and contract monitors, and SDMC staff who are required to know this information to ensure proper trial conduct. Any discussion of study product assignment between pharmacy staff and any other HVTN CRS staff is prohibited. The HVTN SMB members also are unblinded to treatment assignment to conduct review of trial safety.

When a participant leaves the trial prior to study completion, the participant will be told he or she must wait until all participants are unblinded to learn his or her treatment assignment.

In some cases, the CRS, PSRT, or study sponsor may believe unblinding of the site PI and participant would be appropriate to facilitate the clinical management of an AE or SAE. The HVTN Unblinding MOP specifies procedures for emergency unblinding, and for early unblinding for medical reasons.

8 STATISTICAL ANALYSIS

This section describes the final study analyses, unblinded as to treatment arm assignment. All data from enrolled participants will be analyzed according to the initial randomization assignment regardless of how many vaccinations they received. Analyses are modified intent-to-treat in that individuals who are randomized but not enrolled do not contribute data and hence are excluded. Because of blinding and the brief length of time between randomization and enrollment—typically no more than 4 working days—very few such individuals are expected.

Analyses for primary endpoints will be performed using SAS and R. All other descriptive and inferential statistical analyses will be performed using SAS, StatXact, or R statistical software.

No formal multiple comparison adjustments will be employed for multiple safety endpoints, multiple primary immunogenicity endpoints, or secondary endpoints. However, multiplicity adjustments will be made for certain immunogenicity assays, as discussed below, when the assay endpoint is viewed as a collection of hypotheses (eg, testing multiple peptide pools to determine a positive response).

8.1 Analysis variables

The analysis variables consist of baseline participant characteristics, safety, and immunogenicity for primary- and secondary-objective analyses.

8.2 Baseline comparability

Treatment arms will be compared for baseline participant characteristics using descriptive statistics.

8.3 Safety/tolerability analysis

Since enrollment of mother-infant pairs is concurrent with the infant receiving the first vaccination, all infants will have received at least 1 vaccination and therefore will provide some safety data.

8.3.1 Reactogenicity

The number and percentage of participants experiencing each type of reactogenicity sign or symptom will be tabulated by severity and treatment arm and the percentages displayed graphically by arm. For a given sign or symptom, each participant's reactogenicity will be counted once under the maximum severity for all injection visits. In addition, to the individual types of events, the maximum severity of local pain or tenderness, induration or erythema, and of systemic symptoms will be calculated. Kruskal-Wallis and Wilcoxon rank sum tests will be used to test for differences in severity between arms.

8.3.2 AEs and SAEs

AEs will be summarized using MedDRA System Organ Class and preferred terms. Tables will show by treatment arm the number and percentage of participants experiencing an AE within a System Organ Class or within preferred term category by severity or by relationship to study

product. For the calculations in these tables, a participant with multiple AEs within a category will be counted once under the maximum severity or the strongest recorded causal relationship to study product. Formal statistical testing comparing arms is not planned since interpretation of differences must rely heavily upon clinical judgment.

A listing of SAEs reported to the DAIDS Regulatory Support Center (RSC) Safety Office will provide details of the events including severity, relationship to study product, time between onset and last vaccination, and number of vaccinations received.

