		Injection schedule in weeks										
Group	N	Week 0	Week 8	Week 16	Week 32	Week 54						
Part A			Initia	al Safety								
		20 mcg	20 mcg	20 mcg	20 mcg	20 mcg						
		CH505TF	CH505TF	CH505TF	CH505TF	CH505TF						
1	5	gp120	gp120	gp120	gp120	gp120						
		+2.5 mcg	+2.5 mcg	+2.5 mcg	+2.5 mcg	+2.5 mcg						
		GLA-SE	GLA-SE	GLA-SE	GLA-SE	GLA-SE						
2	2	Placebo	Placebo	Placebo	Placebo	Placebo						
Part B		Safety Ramp-Up										
		20 mcg	20 mcg	20 mcg	20 mcg	20 mcg						
		CH505TF	CH505TF	CH505TF	CH505TF	CH505TF						
3	2	gp120	gp120	gp120	gp120	gp120						
		+5 mcg	+5 mcg	+5 mcg	+5 mcg	+5 mcg						
		GLA-SE	GLA-SE	GLA-SE	GLA-SE	GLA-SE						
4	2	Placebo	Placebo	Placebo	Placebo	Placebo						
Part C	Immunogenicity of CH505TF Recombinant Protein											
		20 mcg	20 mcg	20 mcg	20 mcg	20 mcg						
		CH505TF	CH505TF	CH505TF	CH505TF	CH505TF						
5	16	gp120	gp120	gp120	gp120	gp120						
		+5 mcg	+5 mcg	+5 mcg	+5 mcg	+5 mcg						
		GLA-SE	GLA-SE	GLA-SE	GLA-SE	GLA-SE						
6	3	Placebo	Placebo	Placebo	Placebo	Placebo						
		5 mcg	5 mcg	5 mcg	5 mcg	5 mcg						
		CH505TF	CH505TF	CH505TF	CH505TF	CH505TF						
7	5	gp120	gp120	gp120	gp120	gp120						
		+5 mcg	+5 mcg	+5 mcg	+5 mcg	+5 mcg						
		GLA-SE	GLA-SE	GLA-SE	GLA-SE	GLA-SE						
8	3	Placebo	Placebo	Placebo	Placebo	Placebo						
Total	38	28 vaccinees,	10 placebos									

Notes: To ensure safety, enrollment will proceed in stages, see Section 11.3.1. Groups 3 and 5 (20 mcg CH505TF and 5 mcg GLA-SE) and Groups 2, 4, 6, and 8 (placebo) will be pooled in the ultimate analyses.

Participants

Healthy HIV-1—uninfected infants born to HIV-1—infected mothers through caesarian delivery in South Africa. To quantify maternal HIV antibody response, mothers will also be enrolled in the study but will not receive study product.

Sample size

38 mother-infant pairs

Design

Single center, double-blind, randomized, controlled trial

Duration per participant

24.5 months of scheduled clinic visits

Estimated total study duration

32 months (includes enrollment, planned safety holds, and follow-up)

Clinical trial sponsor

DAIDS, NIAID, NIH, DHHS (Bethesda, Maryland, USA)

Study product providers

- CH505TF gp120: DAIDS, NIAID, NIH, DHHS (Bethesda, Maryland, USA)
- GLA-SE adjuvant: DAIDS, NIAID, NIH, DHHS (Bethesda, Maryland, USA)

Core operations

HVTN Vaccine Leadership Group/Core Operations Center, Fred Hutchinson Cancer Research Center (Fred Hutch) (Seattle, Washington, USA)

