4.4.5 Schedule

In this study, the CH505TF gp120 vaccine will be given at 0, 8, 16, 32, and 54 weeks. The first dose will be given within the first five days of life and, to avoid potential confounding of reactogenicity assessments, subsequent boosts will be given at least 7 days after scheduled EPI vaccinations (see Table 4-2). If an infant is found to have delayed EPI vaccinations, those vaccines will be administered by

the site as soon as possible, followed by the next scheduled study product administration no sooner than 7 days later. The boost at week 54 is proposed to guide affinity maturation and the potential development of bnAb B cell lineages.

This schedule is informed by the results of the PACTG 230 study (see Section 4.8.3). The PACTG 230 study immunized infants at 0, 4, 12, 20 weeks (extended schedule) and at 0, 2, 8 and 20 weeks (accelerated schedule) –both with high titers of antibodies that were similar at weeks 24 and 52 (42). A recent infant NHP immunization study comparing three accelerated (0, 3, and 6 weeks) dosing Env arms (protein only, MVA/protein prime boost, combination MVA/protein) vs. a fourth extended dosing (0, 6, 12 and 32 weeks) Env regimen (combination MVA/protein) demonstrated highest avidity antibody in the extended dosing arm (43). In vaccine studies with adult macaques, higher avidity anti-Env antibodies have been correlated with protection against rectal and vaginal simian-human immunodeficiency virus (SHIV) or simian immunodeficiency virus (SIV) challenge (44-47).

Table 4-2 Relationship of HVTN 135 Study Product Administration Schedule to National EPI schedule in South Africa

Infant Age	Vaccine	Proposed Schedule in HVTN 135
Birth	Oral Polio (OPV) Tuberculosis (BCG)	
Day 5		Dose 1
Week 6	Oral Polio (OPV) Rotavirus (RV) Diphtheria-tetanus-acellular pertussis-injectable polio- Haemophilus influenza B Hepatitis B (DTaP-IPV-Hib-Hep B) Pneumococcal Conjugate Vaccine (PCV)	
Week 8		Dose 2
Week 10	Diphtheria-tetanus-acellular pertussis-injectable polio- Haemophilus influenza B Hepatitis B (DTaP-IPV-Hib-Hep B)	
Week 14	Rotavirus (RTV) Diphtheria-tetanus-acellular pertussis-injectable polio- Haemophilus influenza B Hepatitis B (DTaP-IPV-Hib-Hep B) Pneumococcal Conjugate (PCV)	
Week 16		Dose 3
Week 24	Measles Vaccine	
Week 32		Dose 4
Week 36	Pneumococcal Conjugate (PCV)	
Week 52	Measles Vaccine	
Week 54		Dose 5

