6.4.3.2 AEs and SAEs

AEs will be summarized using MedDRA System Organ Class and preferred terms. Tables will show by treatment arm the number and percentage of participants experiencing an AE within a System Organ Class or within preferred term category by severity or by relationship to study product. For the calculations in these tables, a participant with multiple AEs within a category will be counted once under the maximum severity or the strongest recorded causal relationship to study product. Formal statistical testing comparing arms is not planned since interpretation of differences must rely heavily upon clinical judgment.

A listing of SAEs reported to the DAIDS Regulatory Support Center (RSC) Safety Office will provide details of the events including severity, relationship to study product, time between onset and last vaccination, and number of vaccinations received.

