9.4 Follow-up visits, Infants

The following procedures are performed at all scheduled follow-up visits:

• Assessment of new or continuing concomitant medications (as described in Section 9.2)

- Assessment of new or unresolved AEs/intercurrent illnesses.
- Blood collection
- Feeding History

Additional procedures will be performed at scheduled follow-up visits as specified in Appendix D and Appendix F:

- Laboratory tests, including:
 - Complete blood count (CBC)
 - Chemistry panel (ALT, Creatinine)
- HIV infection assessment including pretest counseling and HIV testing. A subsequent follow-up contact is conducted to provide post-test counseling and to report results to participant
- Abbreviated physical examination including weight, vital signs, and a symptom-directed evaluation by history and/or appropriate physical exam based on the mother's reported symptoms for her infant
- Complete physical examination, see HVTN 135 SSP for details
- Stool specimen collection, optional

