9.5 Env-specific B-cell Phenotyping (BCP)

The Env-Specific B cell Phenotyping (BCP) assay will be used to identify and characterize HIV-1 Env-specific B cells and plasmablasts induced by vaccination. The BCP analysis corresponds to

the primary objective to determine whether vaccination with CH505TF gp120 adjuvanted with GLA-SE initiates B-cell lineages potentially capable of generating a broadly neutralizing antibody response. HVTN135 study design will also allow for the comparison infant and adult immune responses to CH505TF gp120 as it mimics the design of HVTN115 that evaluated CH505TF gp120 in adult humans. The study will evaluate two dose levels of the vaccine (20 and 5 mcg) and two dose levels of the adjuvant (2.5 and 5 mcg) given at five time points over 54 weeks. The study consists of 38 total participants: 28 vaccinees and 10 placebo recipients. All vaccines as well as the placebo will be delivered via intramuscular injection (IM).

Samples from baseline (Obtained from cord blood), visit 8 and visit 12 from the maximum of 38 infants in the protocol will be assayed as part of this study.

HIV-1 Env-specific B cells induced by vaccination were identified and characterized using fluorescently-labeled recombinant Env proteins in the context of a flow cytometry panel to identify and characterize those B cells.

Total B cells are identified using doublet exclusion, lymphocyte scatter profile, a viability dye to exclude dead cells, and are negative for lineage markers: CD3, CD56 and CD14; and positive for CD19 and CD20. B cells are further gated as IgD-, then IgG+, and IgA+.

Data from Low IgD- B cells (<5000) and assay results deemed unreliable for analysis by the lab were excluded from the analysis.

To assess positivity for the detection of IgD-, IgG+, and IgA+ B cells, the 85th percentile of the proportion of cells in the subset was calculated, among all placebo recipients (C2+C4+C6+C8) for a given cell subset and visit (visits 8 and 12) and used as the threshold for defining a positive response. Positivity was not assessed for visit 1.

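### Unsolicited AEs are summarised only as ever affected over about 24.5 months, so in common categories the any-grade row can hide a transient excess after vaccination

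*SAP*

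**What the plan says.** The AE analysis is worded alike in Protocol 6.4.3.2 and SAP 8.3.2. The Protocol says: "Tables will show by treatment arm the number and percentage of participants experiencing an AE within a System Organ Class", with a split by severity or by relationship to study product. On repeated events the SAP says that "a participant with multiple AEs within a category will be counted once under the maximum severity", or under the strongest recorded relationship. No test between arms is intended: "Formal statistical testing comparing arms is not planned since interpretation of differences must rely heavily upon clinical judgment".

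Neither section names an observation period. The period follows from collection. Protocol 9.4 lists "Assessment of new or unresolved AEs/intercurrent illnesses" at all scheduled follow-up visits, Appendix F marks it from day 0 to day 743, and the Overview (Protocol Section 3) gives "24.5 months of scheduled clinic visits". On dosing, Protocol 4.4.5 says that "the CH505TF gp120 vaccine will be given at 0, 8, 16, 32, and 54 weeks". SAP 9.5 gives "38 total participants: 28 vaccinees and 10 placebo recipients".

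Timing relative to dose is kept in three other places:

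- Solicited reactogenicity covers 7 full days after each dose (Protocol 9.7). It is tabulated separately and tested between arms (SAP 8.3.1).
- Laboratory values of Grade 1 or above are tabulated by arm at each postvaccination timepoint (SAP 8.3.3).
- The SAE listing gives the time from last vaccination to onset (SAP 8.3.2).

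Under Protocol 9.7, an event that is not on the reactogenicity form, or that starts after day 7, goes to the adverse experience log. If it is a non-serious clinical event, its only planned summary is the untimed table.

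**The concern.** Safety is primary objective 1. Protocol 6.1 justifies a larger placebo group by a high background of serious events in infants, so the randomised contrast is meant to help separate vaccine effects from background. A once-ever percentage over two years weakens that contrast for a category in which most infants have an event anyway. An infant whose only vaccine-related episode falls in a category already counted for an unrelated episode months later adds nothing to the any-grade row. At stake is whether a reader of the final safety table could see a short-lived excess of ordinary, non-serious illness after injection.

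**Working it through.** **The plan's own safety figures.** Protocol 6.1.1 gives no figure for AE percentages or dilution, but its detection statements can be checked.

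- n = 18, true rate 12%: 1 − 0.88^18 = 90.0% chance of at least one event (stated 90%).
- n = 18, true rate 0.58%: 0.9942^18 = 90.1% chance of none (stated 90%).
- n = 10, true rate 20%: 1 − 0.80^10 = 89.3% (stated 90% in the text, 89.3 in Table 6-1).
- n = 10, true rate 1%: 0.99^10 = 90.4% chance of none (stated 90%).

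These reproduce. They concern seeing an event at all, not separating arms against a background.

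**Inputs from the documents.** Final visit target day 743, so T = 743/365.25 = 2.034 years. Five doses.

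**Assumed inputs.** A constant background rate r per infant-year in a category (0.2 to 2 shown); a 28-day window after each dose, so w = 5 × 28 = 140 days = 0.383 years, or 19% of T; a doubled rate in the vaccine arm inside those windows only; full follow-up and all five doses.

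**Formulas** (Poisson, at least one event):

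- Whole study: placebo 1 − exp(−rT); vaccine 1 − exp(−r(T + w)).
- Windowed: placebo 1 − exp(−rw); vaccine 1 − exp(−2rw).

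Worked at r = 2. Whole study: placebo 1 − exp(−4.068) = 98.3%, vaccine 1 − exp(−4.835) = 99.2%. Windowed: placebo 1 − exp(−0.767) = 53.5%, vaccine 1 − exp(−1.533) = 78.4%.

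| r per year | Whole study, placebo vs vaccine (%) | Difference | Windowed, placebo vs vaccine (%) | Difference | Share kept |
|---|---|---|---|---|---|
| 0.2 | 33.4 vs 38.3 | 4.9 | 7.4 vs 14.2 | 6.8 | 72% |
| 0.5 | 63.8 vs 70.1 | 6.3 | 17.4 vs 31.8 | 14.4 | 44% |
| 1 | 86.9 vs 91.1 | 4.2 | 31.8 vs 53.5 | 21.7 | 19% |
| 2 | 98.3 vs 99.2 | 0.9 | 53.5 vs 78.4 | 24.9 | 4% |

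The share kept simplifies to exp(−r(T − w)), with T − w = 603 days = 1.651 years. It is the chance that an infant has no background event outside the windows, and it does not depend on the size of the vaccine effect. At r = 1, exp(−1.651) = 19%.

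**Where the row saturates.** 1 − exp(−rT) reaches 50% at 0.34 episodes per infant-year, 90% at 1.13 and 99% at 2.26.

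**Severity rows.** If 5% of episodes in a 2-per-year category are grade 3 or higher (assumed), that row has r = 0.1: 18.4 vs 21.5% whole study and 3.8 vs 7.4% windowed. About 85% of the difference is kept.

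**Discrimination at 28 vs 10.** For scale only, since no AE test is planned, the exact power of a two-sided Fisher test at 0.05 on the windowed table is 28% at r = 2, 13% at r = 1 and 0.5% at r = 0.2. On the whole-study table at r = 2 it is 0.1%.

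**The case against.** The strongest reply is that much of the post-dose signal is already captured with timing. Reactogenicity is solicited for 7 days after every dose and tested between arms, laboratory grades are shown by timepoint, and SAEs are listed with time since last dose. AE tables are split by relationship, and SAP Section 5 names that assessment as the safeguard against chance imbalance. Severity rows for uncommon grades do not saturate. The SMB sees unblinded data about every 4 months, and the PSRT reviews safety weekly during the injection phase. The placebo group was enlarged because of an 18% SAE rate, not because of common illness. With 10 placebo infants, even a windowed table discriminates poorly.

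Most of this stands, and it confines the point to unsolicited, non-serious clinical AEs. A reader might infer that nothing links non-serious events to the injections; the reactogenicity, laboratory and relationship outputs show otherwise. A reader might also infer that common illnesses will approach 100% in both arms and that any excess will all but vanish. The documents do not support that as a general statement: they give no background rate for common infant illness, and the near-total loss appears only at about 2 episodes per infant-year or more.

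The reply does not close the remaining gap. Relationship is judged case by case, whereas the placebo arm allows a comparison that does not depend on that judgement.

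The SAP Overview limits that document to immunogenicity reports, so its silence does not prove that the safety report lacks a windowed table. Protocol 6.4.3.2 is equally silent.

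**Conclusion.** The point holds for unsolicited non-serious clinical AEs. Under the stated model, the any-grade row keeps about 4% of the windowed difference at 2 episodes per infant-year, 19% at 1, 44% at 0.5 and 72% at 0.2. Which of these applies is unknown from the documents; the higher rates are more plausible for a broad System Organ Class than for a single preferred term. The result rests on the assumed rates, a constant background, the illustrative 28-day window and full follow-up. The 24.5-month period is inferred from the collection schedule, since neither AE section states it. The effect is on descriptive reading of primary objective 1; no error rate or power claim in the plan is affected. This is a cheap improvement, not a flaw that undermines the safety analysis.

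**What to change.** Keep the whole-study table and state its period. In Protocol 6.4.3.2, SAP 8.3.2 and whichever document governs the safety report, add for unsolicited AEs:

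- the same tables limited to onset within a prespecified window after any dose, and the same tables for the remaining time;
- event counts and rates per infant-time by arm for each System Organ Class, in both periods. Rates also allow for missed doses and early termination.

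The sponsor sets the window length; 28 days is only an illustration here. The rule should cover overlap. Under Appendix I, dose 2 may fall as late as day 56 + 14 = 70 and dose 3 as early as day 112 − 21 = 91, which is 21 days apart, so overlapping days should be counted once.

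The cost is extra tables and a window length fixed before unblinding. No new data are needed, provided AE onset and dosing dates are recorded. The added tables remain descriptive, with limited discrimination at 28 against 10.
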